### Summary of Changes – Protocol

#	Date	Change
1.	12/29/2020	
Expand date range of patient history primary objective variables to be captured:
 

- Change cervical cancer screening history interval from 12 months pre-randomization, to most recent screen pre-randomization screen or date of health care system enrollment

- Preventative services history from 10 years pre-randomization to 16 years pre-randomization

- Add COVID testing/history

2.	8/16/2021	Addition of sub-study of optimized and age-tailored educational brochures.
3.		
4.		
5.		

## 1. BACKGROUND

### 1.1 Study Disease(s)

In August 2018, the US Preventive Services Task Force (USPSTF) released updated cervical cancer screening guidelines that include human papillomavirus (HPV) testing alone (i.e., primary HPV screening) as a newly recommended strategy for people with a cervix aged 30-65 years. With primary HPV screening, *home-based screening is an emerging option*, because HPV tests (unlike Pap tests) can be performed on clinician- or self-collected samples. Self-collected samples are as sensitive as clinician-collected samples for detecting HPV and mailing HPV self-sampling kits increases screening participation. Australia and the Netherlands—the first countries to implement primary HPV screening—have HPV self-sampling options. As US healthcare systems prepare to implement primary HPV screening, they will need to consider a variety of strategies

Our recent pragmatic trial at Kaiser Permanente Washington (KPWA) found that mailing HPV self-sampling kits to overdue individuals increased screening uptake by 50% compared to usual care. Nonetheless, screening remained low in both arms, 30% of HPV-positive individuals did not attend follow-up, and we noted gaps in patient understanding of HPV testing. With the USPSTF guideline update, we have a timely opportunity to optimize how health systems *offer* HPV self-sampling outreach to Overdue individuals and test HPV self-sampling outreach approaches among non-Overdue individuals (i.e., those who have successfully screened in the past and are now due). To date, HPV self-sampling randomized clinical trials (RCTs) in the US have included only Overdue individuals; no study has evaluated uptake of HPV self-sampling kits as an alternative to in-clinic screening in a screening-adherent population. Evaluating the cost-effectiveness of different approaches to offering HPV self-sampling kits (e.g., directly mailing kits to all vs. informing individuals about kit availability so they can Opt-In and request the kit) to different health system populations is also an important component of optimizing this strategy.

### 1.2 Rationale

Pap screening has reduced cervical cancer incidence and mortality by >50% over the last 40 years. Nearly all cervical cancer can be prevented by identifying and removing precancers caused by high-risk HPV. However, US adherence to guideline-recommended screening intervals has declined from a high of 82% in 2003 to 74% in 2016. *Increasing screening coverage is a top national priority for cervical cancer prevention.* Well-documented barriers include sociodemographic factors (e.g., race and ethnicity and insurance), knowledge about HPV and cervical cancer, beliefs about importance of regular screening, discomfort/embarrassment with the Pap procedure, and scheduling/time barriers. Individuals who never or rarely screen are a clear intervention priority, as >50% of the 12,000 cervical cancers diagnosed annually are in people who have not been recently screened. At the same time, keeping people engaged in routine screening is critical; in 2017, only 48% of KPWA individuals who were up-to-date with Pap testing attended screening within 6 months after their next due date. HPV vaccinations will not end the need for cervical cancer screening, since current vaccines do not protect against all cancer-associated HPV types. Identifying new, patient-centered options that motivate continued screening initiation and completion is essential now and in the future.

## 2. OBJECTIVES

### 2.1 Primary Objective

To compare cervical cancer screening completion within six months after randomization among individuals randomized to different outreach approaches, stratified by three categories of prior screening behavior:

- A) ***Screening-adherent and coming due:***
  - Outreach #1: Usual care
  - Outreach #2: Usual care + Education (hereafter referred to as “Education”)
  - Outreach #3: Usual Care + Education + Opt-In to request an HPV self-sampling kit (hereafter referred to as “Opt-In”)
  - Outreach #4: Usual Care + Education + Direct Mail HPV self-sampling kit (hereafter referred to as “Direct Mail”)
- B) ***Screen Overdue:***
  - Outreach #1: Usual care
  - Outreach #2: Education
  - Outreach #4: Direct Mail
- C) ***Unknown Prior Screening Behavior:***
  - Outreach #1: Usual care
  - Outreach #2: Education
  - Outreach #3: Opt-In

**Primary outcome**

- Screening completion (*returning the HPV self-sampling kit and attending the recommended in-clinic follow-up screen (if applicable); or receiving in-clinic screening*) within 6 months of randomization

**Secondary outcomes**

[figure not shown]
- Screening initiation (*returning the HPV self-sampling kit or receiving in-clinic screening*) within 6 months of randomization
- Time from randomization to screening completion
- Completion of recommended follow-up after a positive HPV self-sampling kit result (per current guidelines, in-clinic Pap after other-HR HPV positive; or colposcopy after HPV 16/18+)
- Initial screening method (none, HPV self-sampling kit, in-clinic)

The main analysis of primary and secondary outcomes will assess differences between Education, Direct Mail and Opt-In, depending on prior screening behavior. Secondary analyses will assess the benefit of education materials alone, by directly comparing Education to Usual Care.

## **2.2 Secondary Objectives**

- 2.2.1. Evaluate the incremental cost-effectiveness by outreach approach and by prior screening behavior. The outcome will be the incremental cost effectiveness ratio, which will be defined for each outreach approach compared to Education.
- 2.2.2. Identify patient preference for, and satisfaction with, in-home HPV screening and barriers to follow-up of abnormal screening results (1:1 qualitative interviews and focus groups).

**Schema FIGURE 1: Self-Testing Options in the era of Primary HPV screening for cervical cancer**

### 3. PATIENT SELECTION

#### 3.1 Eligibility Criteria

- Currently enrolled at Kaiser Permanente Washington
- Female sex
- 30 years to 64 years of age
- Intact cervix
- Have a primary care provider at Kaiser Permanente Washington
- Due for cervical cancer screening

#### 3.2 Exclusion Criteria

- Flagged by the delivery system as being on a non-routine screening schedule
- Previously randomized to the intervention arm of the HOME trial or invited to the PATH study (P50 CA244432) (participants from the PATH study and individuals randomized to the intervention arm in the HOME trial are excluded from STEP because their prior inclusion in a cervical cancer-related research study could influence their screening uptake and affect the outcome of this trial.)
- On "do not contact list" for research studies
- Currently pregnant or had a pregnancy-related procedure within prior 3 months
- Language interpreter needed

#### 3.3 Inclusion of Women and Minorities

The primary goal of the proposed research is to study whether a programmatic in-home HPV screening outreach strategy improves cervical cancer screening uptake. Because cervical cancer only affects people with a uterine cervix, our entire study population will be composed of female sex individuals. Race and ethnicity are not eligibility requirements for participation in our study. All Kaiser Permanente Washington members who meet our study eligibility requirements will be eligible for random selection

into the study. The ethnic/racial composition of our study population will therefore largely reflect the ethnic/racial composition of Kaiser Permanente Washington female members. The projected proportions of participants from different ethnic/racial backgrounds are based on the composition of Kaiser Permanente Washington members (See Planned Enrollment Report table in Section 5.1).

For the secondary objective (2.2.2) focus groups, we will oversample across non-white race categories to prioritize having at least 60-80% non-white participants overall if possible. For the secondary objective (2.2.2) qualitative interviews, the number of eligible (HPV self-sampling kit positive) individuals is expected to be insufficient to oversample based on race and/or ethnicity. As such, the ethnic/racial composition will largely reflect the ethnic/racial composition of Kaiser Permanente Washington female members.

### **3.4 Inclusion of Children**

We are not enrolling individuals younger than age 30. As of 2020, USPSTF cervical cancer screening guideline recommendations include primary HPV screening only for individuals ages 30 years and older. USPSTF guidelines recommend Pap alone for screening individuals ages 21 to 29. Thus, no participants under age 30 and no children will be included in the study.

## **4. STUDY PROCEDURES**

### **4.1 Subject Recruitment and Screening**

#### **4.1.1 Primary objective (2.1), and secondary objective (2.2.1)**

Under a waiver of consent and HIPAA authorization, the study programmer will use electronic medical record data from KPWA to identify individuals who are due for cervical cancer screening based on previous screening history:

- 1) *Screening-adherent and coming due* (previously screened and due for screening within three months);
- 2) *Overdue* (never screened; or HPV and Pap co-test >5.25 years ago [or Pap alone >3.25 years ago]; or no past Pap and continuously enrolled at KPWA for ≥3.25 years)\*; and
- 3) *Unknown Prior Screening* (enrolled ≥6 months and <3.25 years, with no recorded screening history).

[figure not shown]
\*Individuals with due dates falling between March 2020-August 2020 will have randomization delayed for 12 months (March 2021-August 2021), because KPWA halted routine cervical cancer screening during these months of the COVID-19 pandemic. A 12-month delay in randomization of these individuals will (1) allow time for the delivery system to catch-up on the 6-month back log of screening visits, and (2) avoid potential misclassification of individuals as overdue solely due to their temporary inability to screen during the halted screening or due to their potential likely difficulty to schedule a screening visit during the expected surge in catch-up visits.

Clinical outreach provided by KPWA includes sending individuals a reminder letter that they are coming due approximately 60 days before their screening due date (for screening-adherent individuals), or repeat reminders every 60 days for individuals who are overdue (known to be overdue, or with an unknown screening history). The study programmer will use these clinical system outreach letters to identify eligible individuals. Each week, we will identify individuals who meet eligibility criteria and are mailed a clinical outreach letter. Eligible individuals will be identified, and a random sample will be randomized to intervention groups, stratified by screening history, as described below. Randomization will occur weekly over a 14-month recruitment period, and eligible individuals will be enrolled under a waiver of consent.

The study programmer will use SAS software built in simple random sample procedure to randomly select study participants from all eligible individuals, and then randomly allocate participants into Usual Care, Education, or 1 of 2 intervention arms based on prior screening history (See Figure 1). *Screening-adherent* individuals will be randomized to one of 4 arms: Usual Care, Education, Opt-In or Direct Mail. *Overdue* individuals will be randomized to Usual Care, Education, or Direct Mail. *Unknown* individuals will be randomized to Usual Care, Education, or Opt-In. Target sample size estimates are detailed in section 5.1. During study enrollment and follow-up, the electronic randomization sequence will be concealed from all researchers by the study programmer, and allocation will only be revealed as minimally necessary to investigators directly involved in data collection and/or safety monitoring.

In March 2021, investigators decided to embed a sub-study to investigate the impact of age-tailored educational materials on screening uptake. The initial wave/week 1-42 educational materials were reviewed and edited via supplemental PATH study grant funding (P50 CA244432). The materials were studied via focus groups conducted by the PATH research group, results were reviewed and brochures edited by the PATH and STEP study teams, and new non-age-specific "optimized"/edited and age-tailored ( $\leq 45$  and  $>45$  years of age) educational brochures were produced. The sub-study will be implemented from wave/week 43 onward. Individuals randomized to study intervention arms will be stratified by  $\leq 45$  versus  $>45$  years of age, and then randomly allocated 1:1 to either age-tailored or non-age-tailored educational materials (see Figure 2). The study programmer will use the same randomization and concealment procedures for the sub-study stratification and allocation.

**FIGURE 2: STEP mid-study educational brochure allocation for embedded sub-study – optimized and age-targeted**

#### 4.1.2 Secondary objective two (2.2.2): Qualitative Interviews

We will conduct a series of in-depth semi-structured 1:1 interviews among participants randomized to the intervention arms of the main study who returned an HPV self-sampling kit that tested HPV positive. We expect to invite approximately 100 – 150 participants and anticipate enrolling up to 50 for interviews. Each week, the study programmer will identify eligible individuals. Participants will be contacted by telephone and those interested in participating will be administered verbal informed

consent under an IRB approved waiver of written consent.

#### 4.1.3 Secondary objective two (2.2.2): Focus groups

We will conduct a series of focus groups among individuals randomized to the intervention arms of the main study who either did not request/return a kit or returned a kit that tested HPV negative. Each week, the study programmer will identify eligible individuals for recruitment. The programmer will oversample from the study population across non-white race categories to prioritize having at least 60-80% non-white participants overall if possible. Participants will be contacted by telephone and those interested in participating will be administered verbal informed consent under an IRB approved waiver of written consent. We will conduct up to eight focus groups of up to 10 people per group to learn about study participant experiences with the educational materials and the HPV self-sampling kits.

### 4.2 Procedures

#### 4.2.1 Mailings

Individuals randomized to the Usual Care only arm will receive no study materials. Individuals in all other arms will receive the following after randomization:

1. **Introduction letter:** The letter describes the collaboration between our research team and delivery system. For individuals randomized to the Education arm, the letter describes that we are trying to learn how health education materials may help people understand why cervical cancer screening is important. For individuals randomized to the Opt-In or Direct Mail arms, the letter describes that we are trying to learn more about the best ways to offer an in-home cervical cancer screening option as an alternative to screening in a clinic.
2. **Study information sheet:** The study information sheet contains study procedures, potential risks and benefits, measures to protect privacy and confidentiality, and HIPAA compliance. Individuals are informed their participation is voluntary and that they may call a telephone number to “opt-out” of having their individual data included in the research.
3. **Educational Brochure:** Individuals randomized to intervention arms in waves/weeks 1-42 will receive an educational brochure on HPV and cervical cancer that includes information about why screening for cervical cancer is important, key information about HPV and its role in cervical cancer, and different strategies for cervical cancer screening. For the embedded sub-study (wave/week 43 onward), individuals randomized to intervention arms will be stratified by age ( $\leq 45$  versus  $> 45$  years) and then randomly allocated 1:1 to either age-tailored or non-age-tailored educational materials (see Figure 2).
4. **Opt-In or Direct Mail Inserts:** Individuals randomized to the kit arms will receive an informational insert that describes the in-home cervical cancer screening option. Inserts for Opt-In arm participants will additionally include language on how to order a kit.

#### 4.2.2 HPV self-sampling kits

Individuals in the Direct Mail arm will receive their HPV self-sampling kit one week after receiving the above materials. Individuals in the Opt-In arm will receive their HPV self-sampling kit with instructions within a week of requesting a kit. The kit will include a single use COPAN FLOQswab 552C tube with an affixed pre-printed specimen label; biohazard bag with absorbent material; and a postage paid return mailing box. HPV self-sampling kit testing and resulting will follow KPWA's standard HPV sample processes.

#### 4.2.3 Medical records data

We will obtain data from subject electronic medical records including cervical cancer screening/diagnostic/treatment, medical information related to cervical cancer risk factors, health care use (including preventive services), comorbidities and demographic information.

#### 4.2.4 1:1 Qualitative Interviews

The 1:1 telephone interviews will focus on experiences with follow-up procedures for HPV self-sampling kit intervention arm participants whose results were HPV positive. The 30-minute interview will be recorded and transcribed for coding and thematic analyses. Participants will receive \$50 incentive for their participation.

#### 4.2.5 Focus Groups

Focus group discussions will assess participant experiences with the educational material, preferences and satisfaction with the HPV self-sampling kit and barriers to diagnostic testing for those who did not use the kit. A trained facilitator will ask closed-ended items and open-ended questions exploring feelings about self-collection, communication with providers about screenings, and how aspects of the screening process could be more patient-centered. The focus groups will be audio recorded and transcribed for thematic analysis and participants will receive \$75 incentive for participation.

### 4.3 Early Termination

Subjects will not be terminated from the study by the study investigators; however, subjects may choose to decline some or all study procedures. Participants in all arms, except Usual Care only, will be provided a toll-free number that they can call to withdraw consent. All subject withdrawals will be documented in the study database.

## 5. STATISTICAL CONSIDERATIONS

### 5.1 Sample Size

[figure not shown]
Our sample size calculations are based on pairwise comparisons of screening rates and used preliminary data from the KPWA electronic medical record and observed data from the prior HOME trial. Using 2019 KPWA cervical cancer screening data, we estimate 37.1% of screening-adherent, 30.8% of Overdue, and 27.8% of individuals with Unknown screening histories will be screened within 6 months of randomization in the Education arm. Calculations assume a two-sided level 0.05 test, for differences in two proportions.

Our sample size was selected for adequate power to detect meaningful differences in cervical cancer screening rates between outreach strategies within each of the 3 target populations. Meaningful differences were selected based on estimates from the literature and observed data from the HOME trial. Small improvements in screening uptake are important, particularly if cost-effective and patient-centered; thus, the study is powered to detect relatively small differences between groups. Based on prior studies, we anticipate the Direct Mail strategy will have a greater impact on screening uptake than the Opt-In approach compared to Education; therefore, we have powered the study for a larger minimal detectable difference for the Direct Mail effect.

We estimated the sample size necessary to have 80% power to detect a 3% difference between Opt-In and Education and a 5% difference in screening completion between Direct Mail and Education. We anticipate that the Direct Mail strategy will have a larger impact on screening outcomes than the Opt-In approach, therefore we selected a larger detectable difference (and thus a smaller sample size needed)

for the Direct Mail group. However, in the screening-adherent population, we computed the sample sizes needed for the 3% and 5% detectable differences respectively, and based the Education arm on the sample size necessary for the Education versus Opt-In comparison, which was larger than necessary for the Education versus Direct Mail comparison. Thus, we will have 80% power to detect a 4.1% difference for the Education vs. Direct Mail screening completion comparison. We selected sample size in the Usual Care group to detect a difference of 3.0% in screening completion between Usual Care and Education for the Screening-Adherent and Unknown populations. Given the smaller sample sizes in the intervention groups for the Overdue population, we were unable to achieve a least detectable difference (LDD) of 3.0% between Usual Care and Education. With a sample size of N=1398 in the Education group (based on an LDD of 3% for Education vs Direct Mail), we computed the detectable difference for a variety of sample sizes for the Usual Care group. We selected a sample size of N=5592 (4 Usual Care participants for each Education participant), because further increasing the Usual Care group led to diminishing improvements in LDD. This sample size yields a least detectable difference of 3.8%.

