**FIGURE 3: STEP randomization allocation by screening history**

Target sample sizes for each group, stratified by screening history, are shown in Figure 3, and will include randomizing a total of 13,735 Screening-Adherent (3879 Usual Care, 4171 Education, 4171 Opt-In, and 1514 Direct Mail); 8388 Overdue (5592 Usual Care, 1398 Education, and 1398 Direct mail); and 10,500 Unknown (3128 Usual Care, 3686 Education, and 3686 Opt-In).

Study enrollment will occur over a 14-month recruitment period. For all three study populations (Screening-Adherent, Overdue, and Unknown), the number of eligible individuals is estimated to exceed the number needed for the study. Therefore, to reach target sample size over the recruitment period, we will randomly select 231 Screening-Adherent, 142 Overdue, and 1777 Unknown individuals from the pool of all eligible individuals each week, for inclusion in the study. We will allocate each weekly sample to randomization groups as follows: Screening-Adherent (65 Usual Care, 70 Education, 70 Opt-In, and 26 Direct Mail), Overdue (94 Usual Care, 24 Education, and 24 Direct Mail), and Unknown (53 Usual Care, 62 Education, and 62 Opt-In). This sampling strategy maintains a consistent distribution across randomization arms over time, minimizing any potential impacts of temporal trends on group comparisons. If the number of eligible individuals in any given week is lower than the weekly target, the shortfall will be added to the target recruitment sample for the following week.

Beginning with wave 43, each randomization group (except Usual Care) will be further stratified by  $\leq 45$  years and  $>45$  years age groups, and then 1:1 randomized to receive age-targeted or non-age-targeted optimized Education brochure as part of their intervention materials (see Figure 2).

Our sample size estimates were based on data from 2019, before the COVID-19 pandemic which has impacted in-person cervical cancer screening. The sample size and recruitment plan described above is our *a priori* sampling strategy to achieve target sample size over the 14-month recruitment period. However, since the number of eligible individuals will vary with each data pull, and may be impacted by changes to care delivery, we will closely monitor recruitment and make necessary changes to ensure target sample sizes are met. Potential changes include the following:

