All analyses will be stratified by screening history population (Adherent, Overdue, and Unknown). All analyses will be based on the intention to treat principle, with individuals analyzed by the outreach approach arm to which they were randomly assigned. We will first conduct an overall chi-square test to assess differences in observed screening rates among randomization groups. The primary analysis will use a modified Poisson regression modeling approach to estimate the relative risk of screening completion associated with Direct Mail, and Opt-In strategies relative to Education (as appropriate by screening history population). A binary indicator for screening completion within 6 months (yes/no), as defined above, will be the dependent variable. Models will be fit using generalized estimating equations with an independent working correlation structure and robust standard error estimation to account for correlation between participants paneled to the same primary care provider. Models will adjust for baseline characteristics that differ by randomization arm. Models for Overdue participants will also be adjusted for overdue duration (<3 years and  $\geq 3$  years). The analysis for the outcome of screening initiation will use the same methods. The primary analysis will not include the Usual Care group, but secondary analyses will include this group, and will estimate the relative risk of screening outcomes for Education, relative to Usual Care.

Delays in screening impact time in compliance with screening recommendations and can also impact cancer outcomes. Thus, our analysis will also assess the time it takes to complete screening, defined as the number of days between randomization and screening completion, as a secondary outcome. We will use Kaplan-Meier log-rank tests to compare time to screening completion by randomization arm, with follow-up time censored at 6 months for non-completers. Analyses will be stratified by screening history population (Adherent, Overdue, and Unknown).

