To protect against multiple comparisons for analyses among the screening-adherent population (which has 3 intervention groups in the primary analysis), we will use the Fisher protected least-significant difference approach, which requires that pairwise group comparisons are made only if the overall omnibus test of any differences between group is statistically significant. The referent group for all analyses will be Education. When evaluating Opt-In and Direct Mail, the primary interest is in the impact of the mailed-kit interventions. The educational materials may also impact screening rates, but by using Education as the referent group for comparisons, the estimated group differences will be the effect related to the mailed kit.

The secondary analysis comparison between Education and Usual Care will allow estimation of the effect of the educational materials alone.

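### The 80% power for Direct Mail at 4.1 points in the Screening-Adherent population is a pairwise figure that leaves out the planned omnibus gate; through the gate it is about 77%, and the 80% detectable difference is about 4.3 points

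*Combined protocol and SAP*

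**What the plan says.** Section 5.1 gives the basis of the calculation: "Our sample size calculations are based on pairwise comparisons of screening rates". It adds: "Calculations assume a two-sided level 0.05 test, for differences in two proportions". The planned effects follow: "We estimated the sample size necessary to have 80% power to detect a 3% difference between Opt-In and Education and a 5% difference", the second being Direct Mail against Education. The Education rate assumed for Screening-Adherent individuals is 37.1%. The arm sizes, given with Figure 3, are "3879 Usual Care, 4171 Education, 4171 Opt-In, and 1514 Direct Mail". Because the Education arm was sized for the Opt-In contrast, it is larger than the Direct Mail contrast needs, and section 5.1 draws the consequence: "Thus, we will have 80% power to detect a 4.1% difference for the Education vs. Direct Mail screening completion comparison".

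Section 5.3.1 sets the testing rule. An overall chi-square test comes first. The primary model is then to "estimate the relative risk of screening completion associated with Direct Mail, and Opt-In strategies relative to Education", and the Usual Care group is left out of the primary analysis. For the Screening-Adherent population, described as one "which has 3 intervention groups in the primary analysis", the plan uses Fisher's protected least-significant difference, which "requires that pairwise group comparisons are made only if the overall omnibus test of any differences between group is statistically significant".

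**The concern.** Under the rule in section 5.3.1, a kit contrast in this population succeeds only if two tests are significant: the overall test and the contrast's own test. The probability that both are significant cannot exceed the probability for the pairwise test alone. Section 5.1 speaks of the power the study will have, but the figure it gives ignores the first test.

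These are primary comparisons in the largest of the three populations (13,735 of 32,623), so a reader will take 4.1 points as the difference the planned analysis can detect with 80% power. What is at stake is the accuracy of that statement. The point does not arise in the Overdue and Unknown populations, where the primary analysis has a single comparison each.

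**Working it through.** **Inputs.** From section 5.1: Education rate 0.371; N = 4171 Education, 4171 Opt-In, 1514 Direct Mail; two-sided 0.05; planned effects +0.03 (Opt-In) and +0.05 (Direct Mail); stated detectable difference +0.041 (Direct Mail). From section 5.3.1: chi-square gate on three groups, so 2 degrees of freedom. The 0.05 level for the gate is an assumption in line with section 5.1.

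**Step 1: reproduce the stated power.** Pairwise power = Φ(d/SE − 1.96), with SE = √[p₁(1−p₁)/n₁ + p₂(1−p₂)/n₂].

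- Opt-In +3: SE = √(0.371×0.629/4171 + 0.401×0.599/4171) = 0.01066; 0.03/SE = 2.815; power = Φ(0.856) = 80.4%.
- Direct Mail +4.1: SE = √(0.371×0.629/4171 + 0.412×0.588/1514) = 0.01470; 0.041/SE = 2.790; power = Φ(0.830) = 79.7% (80.1% with a pooled variance).
- Direct Mail +5: SE = √(0.371×0.629/4171 + 0.421×0.579/1514) = 0.01473; 0.05/SE = 3.395; power = Φ(1.435) = 92.4%.

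The plan's 80% is reproduced for both contrasts.

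**Step 2: power of the gate.** Noncentrality λ = Σ nᵢ(pᵢ − p̄)² / [p̄(1 − p̄)], with p̄ the weighted mean rate; 2 df, critical value 5.991.

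- +3/+4.1: p̄ = 0.371 + (4171×0.03 + 1514×0.041)/9856 = 0.3900; λ = 11.53; power 87.0%.
- +3/+5: p̄ = 0.371 + (4171×0.03 + 1514×0.05)/9856 = 0.3914; λ = 14.47; power 93.6%.

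**Step 3: power through the gate.** This is P(gate significant and pairwise test significant). The two tests share data, so the joint probability was simulated: 2,000,000 binomial trials per scenario, Pearson chi-square on three arms, then an unpooled z-test against Education.

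| Effects (Opt-In / Direct Mail) | Gate | Opt-In alone | Opt-In gated | Direct Mail alone | Direct Mail gated |
|---|---|---|---|---|---|
| +3 / +4.1 | 87.0% | 80.3% | 77.3% | 79.8% | 77.0% |
| +3 / +5 (planned) | 93.6% | 80.3% | 79.3% | 92.5% | 90.4% |

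**Step 4: detectable difference through the gate.** With Opt-In at +3, Direct Mail at +4.27 points gives 80.1% gated power, so the 80% detectable difference is about 4.3 points. For Opt-In with Direct Mail at +5, 80.0% is reached at 3.03 points, which is in effect the planned 3.

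**Step 5: sensitivity.**
- With the pairwise test on the log relative-risk scale, closer to the planned model, the gated figures are 77.3% (Opt-In) and 77.6% (Direct Mail) at +3/+4.1, and 79.2% and 90.6% at +3/+5.
- Over an assumed Education rate of 30% to 48%, the loss at +3/+4.1 stays between 2.2 and 3.3 points.
- Correlation within primary care provider and covariate adjustment were not modelled.

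**The case against.** The strongest reply is that section 5.1 claims pairwise power, says so, and has it. That stands. A reader might infer that the 80% was miscalculated, but Step 1 reproduces it.

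Second, +4.1 is not a planned effect. The planned pair is +3 and +5, and there Opt-In stays at about 79% and Direct Mail at about 90%. This also stands, and it bars the inference that the Screening-Adherent comparisons are underpowered. What remains is that section 5.1 does state 80% power at 4.1 points, and the planned procedure does not quite deliver it.

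Third, the description of the overall chi-square test in section 5.3.1 could be read as covering all four arms. At +3/+4.1, a four-arm gate would give between 78% and 79% for both contrasts if Usual Care equals Education, and no loss if Usual Care is 3 points lower. The text favours three arms: section 2.1 limits the main analysis to Education, Direct Mail and Opt-In, and section 5.3.1 excludes Usual Care from the primary analysis and counts three groups. Still, the size of the loss depends on this reading.

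Fourth, section 5.3.1 refers further analytic detail to a statistical analysis plan whose text is not in the document reviewed, so the make-up of the gate may already be defined there.

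Finally, uncertainty in the 2019 planning rates may matter as much as a loss of 1 to 3 points. That is fair, and it is a reason to treat the point as minor.

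**Conclusion.** The point holds as a minor restatement of power. The stated 80% for Direct Mail at 4.1 points is right for a two-arm test but omits the gate that section 5.3.1 places before it. Through that gate it is about 77%, a loss of about 3 points, and the 80% detectable difference is about 4.3 points instead of 4.1. At the planned +3/+5 the loss is about 1 point for Opt-In and 2 for Direct Mail.

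The figures assume a three-arm gate at 0.05, Education at 37.1%, the stated arm sizes, Opt-In at +3, unadjusted tests and no clustering. The documents support neither a finding of faulty arithmetic nor one of an inadequate sample: the arm sizes and the design stand.

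**What to change.** In section 5.1, restate the Direct Mail figure for the Screening-Adherent population as about 77% power at 4.1 points, or as 80% power at about 4.3 points, given Opt-In at +3 and the three-arm gate. Add that at the planned +3/+5 the gated power is about 79% for Opt-In and about 90% for Direct Mail. In section 5.3.1, state that the overall test used as the gate in this population compares Education, Opt-In and Direct Mail, unless the separate analysis plan already says so.

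The cost is wording only, with no extra participants. The downside is that the stated figure becomes slightly less favourable and has to carry an assumption about the effect in the other kit arm.
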